1.4 Efficacy endpoints

1.4.1 Primary efficacy endpoint

The primary efficacy endpoint is the composite responder rate at Month 1 using LCL-ILA and LCL-SLA at maximum smile.

A composite responder is defined as a subject who achieves a score of 0 or 1 in lateral canthal line severity, and at least 2 grades improvement from baseline on both the LCL-ILA and LCL-SLA scales, concurrently, at Month 1 for both left and right sides.

1.4.2 Secondary efficacy endpoints

Secondary endpoints include:

(i) Percentage of subjects who achieve a score of 0 or 1 at the same visit for both left and right sides summarized for each post-treatment visit using the LCL-ILA at maximum smile

Doc id

Effective

Version: 1.0

Title 43QM1901 Statistical Analysis Plan US - QM1114-DP - LCL

MA-43263

Effective date: 2021-02-05 13:17

43QM1901 Statistical Analysis Plan US - QM1114-DP - LCL

MA-43263

Doc id

1.5 Safety assessments and endpoints

For details regarding the safety assessments, please refer to the Clinical Study Protocol (CSP) Section 7.2.

Print date:

2021-04-15 15:20

1.5.1 Adverse events

Adverse events (AEs) are to be monitored throughout the course of the study. All AEs reported will be coded using the Medical Dictionary for Regulatory Activities (MedDRA, version in force at the time of database freeze) and classified by MedDRA preferred term (PT) and system organ class (SOC). AEs will be defined as treatment-emergent adverse events (TEAEs) if the AE had an onset time greater than or equal to the time of study treatment. The study period for the purpose of AE collection is defined as the period from the signing of a study specific informed consent to study exit

A two-point scale ("Yes" or "No" response) will be used for the causality assessments. The Treating Investigator should be asked to indicate a response to each of the following questions in the electronic Case Report Form (eCRF:):

- "Do you consider that there is a reasonable possibility that the event may have been caused by the study product?"
- "Do you consider that there is a reasonable possibility that the event may have been caused by the study product injection procedure?"

If either of these questions is answered with a 'Yes', the AE will be considered related.

AE endpoints include incidence and severity of TEAEs.

1.5.2 Laboratory safety tests

Hematology and blood chemistry laboratory tests will be performed at baseline (before treatment) and Month 6. Laboratory safety test endpoints include:

- · Values collected at each visit
- Changes from baseline

1.5.3 Focused physical examination

Physical examination will be done at screening/baseline (before treatment), Day 7, Day 14, Month 1, and Month 6. Normal, abnormal and clinically significant findings will be assessed.

1.5.4 Vital signs

Vital signs will be assessed from baseline (before and after treatment), Day 7, Day 14, Month 1, and Month 6. Vital signs endpoints include:

- Values collected at each visit
- Changes from baseline

1.5.5 Neutralizing antibody testing

Blood samples will be taken for measurement of serum neutralizing antibody testing against QM1114-DP at baseline (before treatment), Month 1, and Month 6. Analysis of the blood samples include in vitro screening and confirmatory (if positive screening result) ELISA assays to test for the presence of binding antibodies, and in vivo mouse protection assay (MPA) to test for the presence of neutralizing antibodies. The MPA will only be conducted if the subject has a positive confirmatory result.

1.5.6 Electrocardiogram (ECG)

ECG recordings will be done at baseline (before treatment), Month 1, and Month 6. The following items will be measured:

Doc id 43QM1901 Statistical Analysis Plan US - QM1114-DP - LCL 🖧 GALDERMA MA-43263

- RR interval
- PR interval
- QRS interval
- QT interval
- Heart rate (HR)
- QTcB interval
- QTcF interval

During each visit where ECG is conducted, the ECG will be recorded in triplicates. In addition to the individual measurements, the above items will be aggregated into a mean value per visit (mean of all beats). ECG endpoints include:

- Aggregated values collected at each visit
- Changes from baseline
- QTcB and QTcF prolongation criteria
- Overall assessment (Normal, Abnormal Not Clinically Significant, Abnormal Clinically Significant) of the ECG

Doc id 43QM1901 Statistical Analysis Plan US - QM1114-DP - LCL 🖧 GALDERMA MA-43263

Print date:

2021-04-15 15:20

2 Statistical Methods

2.1 General methods

All tables, listings, and figures will be programmed using SAS Version 9.4 or higher. Data collected in this study will be documented using summary tables and subject data listings created by using the SAS® system. Confidence intervals (CI) and p-values will be 2-sided and performed at a significance level of 5%, unless otherwise specified. Data for all subjects in the clinical database will be included in the data listings. Calculated (derived) variables will be listed as appropriate. Any changes from the SAP will be detailed in the clinical study report.

All efficacy, safety and baseline characteristics variables will be presented using descriptive statistics within each treatment group, and graphs as appropriate. Continuous variables will be summarized using descriptive statistics (number of observations, mean, standard deviation [SD], median, minimum, and maximum). Categorical variables will be presented in frequency tables with number and percentage of observations for each level. Missing counts for all variables will be presented for informational purposes only and will not be included in percentage calculations.

Study days will be calculated relative to the injection of study drug. Day 0 will be the day of study drug administration. Baseline will be the last assessment prior to the injection of study drug unless otherwise indicated. The Screening Visit 1 (Day -14 to Day 0) will be considered the visit prior to injection of study drug. Because the Screening visit and Baseline visit (Day 0) may be performed on the same day, the Screening visit can also be Day 0.

Adverse events, cosmetic/aesthetic procedures and implant history events, medical history events, and concomitant treatments/procedures will be coded using MedDRA, Version 23.0. Prior/concomitant medications and procedural anesthetics will be coded using the World Health Organization (WHO) Drug Dictionary Global, 1 Sep 2019 B3 or higher.

In general, efficacy, safety, col analyses will be performed and summarized by treatment group (QM114-DP, placebo), unless otherwise stated.

2.1.1 Visit windows

Study visits are expected to occur according to the protocol schedule in Appendix F. All data will be tabulated per the evaluation visit as recorded on the eCRF even if the assessment is outside of the visit window. In data listings, the relative study day (in relation to date of study drug administration) of all dates will be presented. There will not be any windowing for unscheduled visits in the analysis, and unscheduled visits will not be included in any analyses. Unscheduled visits, if any, will be presented in listings only.

Pooling of Centers 2.1.2

As this is a multi-center study, it is possible that some sites may only enroll a small number of subjects. Since this study plans to conduct some site-level analyses, pooling of sites may need to be considered for reliable and accurate results. If any site enrolls less than 5 subjects, then sites will be pooled by the following geographic regions:

- US sites
 - East
 - North
 - South

Doc id 43QM1901 Statistical Analysis Plan US - QM1114-DP - LCL 👶 GALDERMA MA-43263

Print date:

2021-04-15 15:20

West O

Canadian sites

- If only one site exists in this country, then its region will be pooled with the respective US region above (i.e. Canada – East will be pooled with US – East); otherwise sites will be pooled into the following geographic regions:
- East 0
- North 0
- South
- West

This region-level site grouping will then be used for all site-level analyses. This will be done prior to unblinding.

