Demographic Data ³ including, Fitzpatrick skin type, medical history & concurrent diseases, previous facial treatments/procedures (toxin naïve/non-toxin naïve)	x									
Inclusion /Exclusion Criteria	X	X4								
Concomitant Therapies/ Procedures	X	X 5	X	X	X	X	X	X	X	X
Adverse Events	X	X 5	X	X	X	X	X	X	X	X
Urine Pregnancy Test ⁶	X	X 4								X
Vital Signs (blood pressure, heart rate, and respiratory rate)7		X 5	X	X	X					X
ECG		X ⁴			X					X
Blood sample clinical chemistry and hematology		X ⁴								X
Blood sample for serum antibody testing		X ⁴			X					X
ILA of LCL Severity	X	X ⁴	X	X	X	X	X	X	X	X
Focused Physical Examination (face, head, neck) ⁸	X	X4	X	X	X					X
Photography		X4	X	X	X	X	X	X	X	X
Randomization		X 4								
Treatment		X9								
CCI										
Subject assessments										
SLA of LCL Severity ¹⁰	X	X 4	X	X	X	X	X	X	X	X
CCI										

- Screening and baseline visits may be on the same day. If completed on the same day, only perform study assessments 7.
 once (i.e., PE, UPT, SLA, ILA, AE, concomitant therapies/procedures, inclusion/exclusion review)
- 2. If the subject withdraws before the final visit the assessments at Month 6/ET should be completed, if possible.
- 3. Includes date of birth, gender, race, ethnicity, height, and weight.
- 4. To be performed before treatment.

CCI

6. Females of childbearing potential.

Version: 4.0

- Vital signs are taken seated after 10 minutes rest. Vital signs are taken prior to any blood draw (excluding post-treatment measurements on Day 0).
- Post-baseline, events suggestive of remote spread of toxin are also considered while doing clinical evaluations based on the subject's symptoms and signs. Directed questioning and examination will then be performed as appropriate.
- 9. Following treatment administration, subjects will be monitored at the study center for 30 minutes.
- Subjects will make their Lateral Canthal Line assessments independently of the Investigator's assessment.

CONFIDENTIAL Page 18 of 87

Effective date: 2020-06-10 11:38

Doc id 43QM1901 Clinical Study Protocol - QM1114 - LCL ♣ GALDERMA MA-40370

Print date:

2020-06-11 13:03

LIST OF ABBREVIATIONS AND DEFINITIONS OF TERMS

Abbreviation/Term	Definition
°C	Degrees Celsius
AE	Adverse Event
ALP	Alkaline Phosphatase
ALT/ALAT (SGPT)	Alanine Aminotransferase (Serum Glutamic Pyruvic Transaminase)
AST/ASAT (SGOT)	Aspartate Aminotransferase (Serum Glutamic Oxaloacetic Transaminase)
BoNT	Botulinum Toxin
BoNT-A	Botulinum Toxin Type A

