5.5 Procedures/Reasons for Subject Discontinuation

An Investigator may decide to discontinue a subject from the clinical study for safety reasons.

Although the importance of completing the entire clinical study should be explained to the subject by the clinical study personnel, any subject is free to discontinue participation in this clinical study at any time and for whatever reason, specified or unspecified, and without any prejudice. No constraints are to be imposed on the subject, and when appropriate, a subject may be treated with other conventional therapy when clinically indicated.

When a subject does not complete the clinical study, he/she will be fully assessed, if such assessment is possible. The procedures designated for the Month 6/ET visit should be completed for all subjects discontinuing the clinical study and the appropriate eCRF should be completed.

All discontinuations and the reason for discontinuation are to be documented by the Investigator on the exit form. For discontinuation due to an AE, the AE form is to be completed. The Investigator should also ensure that the subject receives suitable therapy for the AE.

Potential reasons for discontinuation are listed below:

Adverse Event: Complete an AE form.

 Withdrawal by Subject:
 Includes consent withdrawal, subject relocation, schedule conflicts, etc.
 Explain the reason for withdrawal in the comment section of the eCRF

exit form.

 Lost to Confirmed with two documented phone calls and a certified letter Follow-up: (delivery receipt requested) without answer. Explain in the comment

section of the eCRF exit form.

Other: This category is to be used for a subject who discontinues due to a

reason other than as specified in the predefined categories above. Explain the reason for discontinuation in the comment section of the

eCRF exit form.

A subject who has been randomized and assigned a kit number/randomization number cannot be replaced by another subject if he/she discontinues the clinical study for any reason. Additional subjects could be enrolled (randomized/assigned to treatment) in order to attain the number of evaluable subjects.

Effective date: 2020-06-10 11:38

Doc id

Print date:

MA-40370

2020-06-11 13:03

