8.1.7 Month 6/Visit 10 or Early Termination visit (±5 days)

At the Final/ET, the Investigator or designee will:

- 1. Ask the subject about AEs using an open-ended question, such as "Have you noticed any change in your health since the last visit?" Record all events, as appropriate.
- 2. Ask the subject about any changes in his/her concomitant therapies/procedures (added, removed or changed) since the previous visit. Record all changes.
- 3. Instruct the subject on how to complete the LCL-SLA at CCI maximum smile. Subject to complete self-assessment of bilateral LCL severity at maximum smile using the 4-point Photographic Scale (Section 7.1.2 and Appendix 2).
- 4. 5.

GALDERMA

Title
43QM1901 Clinical Study Protocol - QM1114 - LCL

MA-40370

Print date:

2020-06-11 13:03

6.	CCI			
7.				

- Obtain the subject's vital signs (blood pressure, heart rate, and respiratory rate). Vital signs are to be taken seated after 10 minutes rest (Section 7.2.2).
- Obtain 12-lead ECG recording after the subject has been resting in a supine position for at least 10 minutes (Section 7.2.3).
- Collect blood sample (chemistry and hematology) for analysis at the central laboratory (Section 7.2.4).
- 11. Collect blood sample for neutralizing antibody testing (Section 7.2.5).
- Take subject photographs (refer to photo manual for complete instructions). If the subject is wearing make-up, instruct the subject to remove it prior to taking photographs.
- If the subject is a female of childbearing potential, collect urine for UPT and complete pregnancy test (see laboratory manual for additional procedures). Document the result.
- Investigator to complete assessment of the subject's bilateral LCL severity at maximum smile using the 4-point Photographic Scale (LCL-ILA) (Section 7.1.1 and Appendix 1).
- Investigator to perform a focused PE (Appendix 6).
- Exit the subject from the study.

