2.4.4 Secondary analysis

To evaluate the effectiveness of QM1114-DP versus placebo in the treatment of moderate to severe LCL, the proportion of subjects who achieve 0 or 1 on the LCL-ILA at maximum smile at Month 1 and at all the rest of the post-treatment visits will be compared using the CMH test, stratified by site. To control the type I error rate, the fixed sequence testing procedure will be used, which requires no adjustment to the level of significance. However, the comparisons must be made in a pre-specified order following the procedure outlined below:

Print date:

2021-04-15 15:20

1. Primary analysis must be done first, prior to any other analysis

Secondary analyses:

- 2. Month 1 responder rate
- 3. Day 14 responder rate
- Month 2 responder rate
- Month 3 responder rate
- Month 4 responder rate
- Month 5 responder rate
- Month 6 responder rate
- Day 7 responder rate

If one of the tests in the sequence is not significant (p > 0.05), no confirmatory claims can be made based on tests following (and including) that one.

The secondary analysis in the sequence will be based on the ITT population with the remote visit assessments excluded. A sensitivity analysis will be conducted using the ITT population including the remote visit assessments.

[figure not shown]
Results will include estimates of the percentages, difference in percentages, 95% CIs, and CMH pvalue as well as a graph showing the percentages for the two treatment groups over time. For consistency across strata, the Breslow-Day test will be used.

Doc id 43QM1901 Statistical Analysis Plan US - QM1114-DP - LCL 🖧 GALDERMA MA-43263

Print date:

2021-04-15 15:20

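### No rule separates early-termination assessments from the shared Month 6/ET visit, so early leavers' results can enter the confirmatory Month 6 responder test

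*SAP*

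**What the plan says.** **One visit, two purposes.** Protocol 8.1.7 is headed "Month 6/Visit 10 or Early Termination visit". A footnote to the Schedule of Assessments (protocol Table 2) reads: "If the subject withdraws before the final visit the assessments at Month 6/ET should be completed, if possible". Protocol 5.5 repeats this: "The procedures designated for the Month 6/ET visit should be completed for all subjects discontinuing the clinical study". The procedures include the LCL-ILA at maximum smile, the variable of the secondary test. SAP Appendix F carries the same combined column.

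**Visit assignment.** SAP 2.1.1 states: "All data will be tabulated per the evaluation visit as recorded on the eCRF even if the assessment is outside of the visit window". The only visit type it removes is the unscheduled one: "unscheduled visits will not be included in any analyses".

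**The test affected.** SAP 2.4.4 places "Month 6 responder rate" in the fixed sequence, after Month 5 and before Day 7. Counting the primary analysis as the first test, it is eighth of nine. SAP 2.4.2 analyses the secondary endpoints as observed cases, without imputation. SAP 2.4.4 uses the ITT population and takes out only remote assessments.

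No visible text in either document reassigns ET assessments by study day, gives them their own analysis visit, or keeps them out of Month 6.

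**The concern.** If an ET assessment is stored under the Visit 10 label, the SAP's rule makes it that subject's Month 6 result, however early it was made. Without that record the observed-case analysis would simply leave the subject out at Month 6.

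The error would not be balanced between arms. Protocol 1.1 says the effect of botulinum toxin type A on facial lines usually lasts about 4-6 months, after which severity returns to baseline. An active subject who leaves in the first few months may therefore still be at grade 0 or 1, while a placebo subject who leaves is unlikely to be. Month 6 is where an early assessment departs most from the true value. At stake are the size of the Month 6 difference, the confirmatory claim at Month 6, and passage to the Day 7 test.

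**Working it through.** **Inputs from the documents.** 225 active and 75 placebo subjects (SAP 2.7.3); two-sided 5% level (SAP 2.1); CMH test (SAP 2.4.4); one month = 28 days (protocol Table 2); Month 6 window ±5 days (protocol 8.1.7). Neither document states a figure for the Month 6 test or a dropout rate in its visible text, so there is no figure of the plan's own to reproduce here.

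**Windows.** Month 6 = 6 × 28 = Day 168, so the window opens on Day 168 − 5 = Day 163. Month 1 = Day 28 ± 5 = Days 23-33.

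**Assumptions.**
- The true Month 6 rate of grade 0/1 is 5% in both arms.
- A share f of the Month 6 records in each arm are early ET assessments: 3%, 5% or 10%.
- Of active ET subjects, a share q is still at grade 0/1: 25%, 50% or 75%. Placebo stays at 5%.

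**Formula.** Recorded active rate = (1 − f) × 5% + f × q. Example with f = 5%, q = 75%: 0.95 × 0.05 + 0.05 × 0.75 = 0.0475 + 0.0375 = 8.5%, a false difference of 3.5 points.

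**Rejection probability.** All outcomes of two binomials (225 and 75) were enumerated with the single-stratum CMH statistic, rejecting when |z| > 1.96.

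| f | q | Recorded active rate | Two-sided rejection |
|---|---|---|---|
| 0 | – | 5.0% | 5.0% |
| 3% | 25% | 5.6% | 4.7% |
| 3% | 50% | 6.35% | 5.5% |
| 3% | 75% | 7.1% | 7.5% |
| 5% | 25% | 6.0% | 4.9% |
| 5% | 50% | 7.25% | 8.0% |
| 5% | 75% | 8.5% | 13.9% |
| 10% | 25% | 7.0% | 7.2% |
| 10% | 50% | 9.5% | 20.4% |
| 10% | 75% | 12.0% | 41.3% |

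At 3% and 5% ET with q = 25%, the two-sided figure does not rise. The small gain in rejections favouring active is offset by fewer rejections favouring placebo.

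**If a true difference exists.** A simulation of 100,000 trials per scenario took true rates of 10% vs 5%, 5% ET, half or all ET visits near the height of effect, and grade 0/1 rates at those visits of 60-80% active and 10% placebo. Counting ET as Month 6 moved the mean difference from 5.0 to 6.1-8.3 points and rejection from about 22% to 33-52%.

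**The case against.** **The labelling is inferred.** The eCRF is not among the documents. Discontinuation is recorded on an exit form, the SAP's analysis sections say Month 6 without ET, and a separate ET form or flag may exist. This stands as a limit on certainty. It does not close the point, because the SAP does not say to use such a flag.

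**The size may be small.** ET assessments are made only where possible, and subjects lost to follow-up would generally have none, so f is smaller than total dropout. Exits can fall at any time, and dissatisfied non-responders may be among the leavers. This also stands: with 25% of active ET subjects still responding, rejection is 4.9% at 5% ET and 7.2% at 10% ET.

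**Stronger readings that a reader might infer, and why they fail.**
- *Month 1 primary data are discarded when a subject exits on Days 23-33.* Not shown: such a visit could be recorded as Visit 5.
- *Early leavers are assessed at peak effect, so false positives reach 39-71%.* Those figures need 15% ET with 50-75% still responding. Nothing in the documents supports that share or defines a peak.
- *The error rate starts from 1.5%.* That is the tail favouring active only. The planned test is two-sided, and its starting value is 5.0%.
- *Antibody results are mislabelled.* SAP 2.5.4 sends them to a separate report.
- *Month 6/ET safety labs are an error.* Protocol 7.2.4 deliberately makes the post-baseline sample a Month 6/ET sample. Only its label in the summaries is at issue.

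**Conclusion.** The gap is real and of moderate severity. As written, the SAP can count an early leaver's LCL-ILA as an observed Month 6 result in a confirmatory test, and the likely direction favours active. Whether it does so depends on how the eCRF stores ET visits, which the documents do not show.

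Under the stated assumptions the effect runs from negligible at 3% ET to material at 10% ET when half or more of active leavers still respond. The rates are assumptions throughout. A reader might infer that the trial's main conclusion is at risk, but the documents do not support that. The primary analysis and the six secondary tests ahead of Month 6 do not use Month 6 data, only Day 7 follows, and the safety analyses are descriptive.

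**What to change.** Add to SAP 2.1.1, before unblinding:

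1. **Efficacy.** Assign an ET assessment by study day to the scheduled visit whose window contains it, and only if that visit has no scheduled value; this settles two assessments in one window. Include Month 1 (Days 23-33) if an exit assessment there was recorded as ET.
2. **Month 6.** Count an ET assessment as Month 6 only from Day 163. Otherwise treat Month 6 as missing. An ET value that falls in no window is listed only.
3. **Labs, ECG and vital signs.** Keep early ET values in the summaries under a separate label such as ET/last post-baseline. Listing them only would be wrong: chemistry and haematology are scheduled only at baseline and Month 6/ET, so an early leaver's only scheduled post-baseline labs would drop out of the summaries.

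If the eCRF already separates ET visits, the SAP should say so and state that the derivation uses that separation.

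The cost is SAP wording and a little derivation code. The Month 6 rate may look less favourable.

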8.2 Unscheduled Visits

When necessary, unscheduled visits may be conducted, in particular if an AE occurs and needs to be assessed and/or treated.

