2.5.5 Physical examinations and vital signs

The number and percentage of subjects with normal/abnormal results in physical examination will be presented by visit and treatment. A shift table will be created to present any change from baseline in normal/abnormal results in physical examination across the study visits for each treatment group.

Vital signs at baseline, Day 7, Day 14, Month 1, and Month 6, and the changes from baseline will be summarized by treatment and visit using descriptive statistics.

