2.5.6 ECG

The aggregated value of each ECG measurement (described in Section 1.5.6) at baseline, Month 1, Month 6, and the changes from baseline will be summarized descriptively by treatment group at each visit. In addition, a shift table will be created to show any change from baseline to Month 6 in the overall ECG assessment.

QTcF and QTcB interval prolongation will be presented separately as well. The number and percentage of subjects with a QTcF and/or QTcB interval of >450 msec, >480 msec, and >500 msec will be summarized by treatment and visit, along with the number and percentage of subjects with a change from baseline in QTcF and/or QTcB interval of 30 - < 60 msec and ≥60 msec.

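### Some collected safety measurements have no place in the SAP's descriptive tables: results from unscheduled visits, the Month 1 overall ECG shift, and the Day 0 post-injection vital signs

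*SAP*

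**What the plan says.** **Unscheduled visits.** SAP 2.1.1 states that "unscheduled visits will not be included in any analyses" and adds: "Unscheduled visits, if any, will be presented in listings only". It makes no exception for safety data, and nothing in SAP 2.5 restores one. Protocol 8.2 explains when such visits arise: "unscheduled visits may be conducted, in particular if an AE occurs and needs to be assessed and/or treated".

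**ECG.** SAP 1.5.6 gives the schedule: "ECG recordings will be done at baseline (before treatment), Month 1, and Month 6". Among the ECG endpoints it names "Overall assessment (Normal, Abnormal Not Clinically Significant, Abnormal Clinically Significant) of the ECG". SAP 2.5.6 summarises the measured intervals and their changes at both post-baseline visits and counts QTcF/QTcB threshold crossings by treatment and visit. For the overall assessment, however, "a shift table will be created to show any change from baseline to Month 6 in the overall ECG assessment".

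**Vital signs.** SAP 1.5.4 says: "Vital signs will be assessed from baseline (before and after treatment), Day 7, Day 14, Month 1, and Month 6". Protocol 8.1.2 requires the post-treatment reading at the baseline visit. SAP 2.5.5 plans the summary as follows: "Vital signs at baseline, Day 7, Day 14, Month 1, and Month 6, and the changes from baseline will be summarized". SAP 2.1 defines baseline as the last assessment before injection.

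**The concern.** Vital signs, ECG and focused examination findings are named safety endpoints in Protocol 2.1.4. If the SAP is programmed as written, part of what is collected on them reaches no table that compares the two arms.

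Adverse event tables do not fully replace those summaries. Under Protocol 7.2.2 and 7.2.3, a vital-sign or ECG change becomes an AE only if it is judged clinically significant. Threshold counts and shift tables are useful because they show measured values without that judgement, and the ECG scale has a separate middle category for abnormal readings judged not clinically significant.

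The schedule gives the unscheduled-visit rule some weight. Table 2 of the protocol plans no ECG, vital signs or focused examination at Months 2 to 5. Between Month 1 and Month 6, apart from an early termination visit, an unscheduled visit is the main way such a measurement would be made.

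**Working it through.** No sample size, power or error rate is involved, and the plan has no figure to reproduce. The check sets the planned post-injection time points beside those that the summaries name.

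| Measurement | Planned after injection | In the summary | Count |
|---|---|---|---|
| ECG intervals, changes and QTc thresholds | Month 1, Month 6 (SAP 1.5.6) | Month 1, Month 6 (SAP 2.5.6) | 2 of 2 |
| Overall ECG assessment, shift table | Month 1, Month 6 (SAP 1.5.6) | Month 6 (SAP 2.5.6) | 1 of 2 |
| Vital signs | Day 0 post-treatment, Day 7, Day 14, Month 1, Month 6 (SAP 1.5.4; Protocol 8.1.2) | Day 7, Day 14, Month 1, Month 6 (SAP 2.5.5) | 4 of 5 |
| Any value measured at an unscheduled visit | As needed (Protocol 8.2) | None; listings only (SAP 2.1.1) | 0 |

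**Unscheduled values.** The QTc categories (above 450, 480 and 500 msec; increases of 30 to under 60 msec and of 60 msec or more) are counted by visit. There is no any-time or worst-value row. With unscheduled visits excluded, a QTc above 500 msec recorded at one of them would enter no count. The same holds for an unscheduled overall ECG reading or focused examination.

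**AE tables.** SAP 1.5.1 defines a TEAE by onset relative to treatment, and SAP 2.5.2 tabulates all TEAEs by system organ class and preferred term, not by visit. An AE found at an unscheduled visit should therefore be counted. Protocol 7.2.1 and Appendix 6 require abnormal examination findings after injection to be recorded as AEs, without the clinical-significance condition that Protocol 7.2.2 and 7.2.3 apply to vital signs and ECG.

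**ECG shift.** SAP 2.5.5 runs the physical examination shift over all study visits. SAP 2.5.6 gives no reason for handling the ECG shift differently.

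**Day 0 vital signs.** Because SAP 2.1 defines baseline as pre-injection, the post-treatment reading cannot be the baseline row, and no other row in SAP 2.5.5 fits it. SAP 1.5.4 makes the values at each visit and their changes endpoints. Protocol 9.1.3.2 plans vital signs at each visit with change from baseline and makes no exception for this reading. SAP 2.8 is meant to set out all departures from the protocol and lists only the per-protocol sensitivity analysis.

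**The case against.** The strongest reply is that these are small descriptive omissions with other cover. Keeping irregular visits out of by-visit tables is ordinary and defensible. Any unscheduled value is still listed. Protocol 8.2 prescribes no ECG, vital signs or examination at such a visit, so the number of affected values is unknown and may be nil. ECGs go to a central reviewer, and readings flagged as clinically significant trigger an alert (Protocol 7.2.3). Suspected toxin-spread and hypersensitivity events have their own tables (SAP 2.5.2.2). SAP 2.1 says in general that safety variables will be presented, so a Month 1 frequency table of the overall ECG assessment may be produced anyway. The word baseline in SAP 2.5.5 could also be read as the whole visit, covering both Day 0 readings.

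Most of this stands as a limit on size, and it rules out several stronger readings that a reader might infer:

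- *That adverse events found at unscheduled visits are dropped.* The wording of SAP 2.1.1 is broad enough to suggest it, but the TEAE definition and tables do not depend on visit.
- *That AE reporting captures only clinically significant findings.* This is not so for the focused examination.
- *That a transient Month 1 ECG abnormality would leave a clean table.* Month 1 intervals, changes and QTc counts are all summarised. Only the shift in the three-level assessment is missing.
- *That Month 6 is too late for the ECG because muscle function has returned.* Protocol 1.1 speaks of facial muscles and says nothing about cardiac timing.
- *That the omitted data are the ones most likely to show harm.* Neither document supports that ranking.
- *That the SAP expressly excludes the Day 0 post-treatment vital signs.* SAP 2.5.5 fails to name them, which is an inconsistency and not a rule.

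The reply does not remove the gaps. Listings do not compare arms, the general sentence in SAP 2.1 does not supply the missing shift, and the visit reading of baseline conflicts with the SAP's own definition.

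**Conclusion.** The concern holds in a limited form. Followed as written, the SAP keeps all measured results from unscheduled visits out of its tables, uses 1 of 2 planned post-baseline assessments in the overall ECG shift, and names 4 of 5 planned post-injection vital-sign readings. These counts describe table coverage and are not an estimate of missed harm. The documents do not show how many unscheduled measurements there would be.

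The conclusion rests on reading SAP 2.1.1 literally for measured values and on SAP 2.1's pre-injection definition of baseline. It also assumes that AE tables are built by onset time as SAP 1.5.1 and 2.5.2 describe. It affects descriptive safety reporting only. The change is worth making because the endpoints are named ones and the cost is very low.

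**What to change.** - **SAP 2.1.1:** limit the exclusion of unscheduled visits to by-visit summaries, and state that AE tables are unaffected. Count unscheduled post-injection values in an any/worst post-baseline row for the QTc categories, the overall ECG assessment and the focused examination.
- **SAP 2.5.6:** add the baseline-to-Month 1 shift in the overall ECG assessment.
- **SAP 2.5.5:** add a Day 0 post-treatment row for vital signs, with change from the pre-injection value, so that the section agrees with SAP 1.5.4 and Protocol 8.1.2 and 9.1.3.2. If the omission is deliberate, record it with a reason in SAP 2.8.

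The cost is some SAP wording and a few descriptive table rows. No new data or procedure is needed, and no confirmatory analysis or AE count changes.
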